Ocular assessments including Best Corrected Visual Acuity (BCVA) by Early Treatment Diabetic Retinopathy Study method (ETDRS), slit lamp biomicroscopy, intraocular pressure (IOP), fundoscopy, color fundus photography (FP), fluorescein angiography (FA), B-scan ultrasound (B-scan), A-scan ultrasound (A-scan), enhanced depth imaging optical coherence tomography (EDI-OCT), optical coherence tomography angiography (OCTA), and visual fields will be evaluated during the study. Phlebotomy will be performed at various time points for hematology, serum chemistry and anti-drug antibodies (ADA). Concomitant medications and adverse events (AEs) will be reviewed through 30 days following the study treatment. After 30 days, for Cohorts 1 to 9, only AEs or SAEs determined by the Investigator to be related to study product and/or study procedures are to be reported. For Cohort 10, 11 and 12 subjects, concomitant medications and all adverse events will be reviewed through their last study visit. If peri-tumoral whitening/pigmentary changes are seen during the study, additional assessments as outlined in Section 10.3.10 should be conducted. Further treatment (additional therapy) for CM

will be documented throughout the study. Section 10 provides further details on the conduct of the study, study visits, and assessments.

Ocular imaging, including B-scan, A-scan, FP, FA, EDI-OCT, and OCTA will be read by a centralized Independent Reading Center (IRC) to provide consistency and reliability in data generated for each subject at each study site. At least two independent readers at the IRC will review required screening B-scan images for determination of eligibility and at the predefined time points.

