The intention is to alternate the enrollment of Cohorts 10 and 11. If during the enrollment of these subjects, a subject has just been enrolled into Cohort 11 and a subject with documented growth presents, then that subject may instead be enrolled into Cohort 11 rather than Cohort 10 for which they would not be eligible due to the presence of documented growth and instead will be assigned to receive the first of 2 cycles of AU-011.

If 2 subjects experience a DLT during treatment with Cycle 2, as defined in Section 8.4.1., then no further subjects will receive Cycle 2 of AU-011 until discussed with the independent ocular oncologist and medical monitor and continuation of enrollment is confirmed.

Subjects with Documented Growth

Enrollment in Cohorts 10 and 11 was closed following approval of protocol revision 11 (Rev-11) at each site. An additional cohort, Cohort 12, of subjects with minimum defined levels of documented growth will be initiated to allow assessment of safety and efficacy of 2 cycles of AU-011 treatment in this key subgroup of subjects with CM. Since Cohort 12 has the same dose as Cohort 11 no additional safety review will be required prior to initiating this cohort.

Up to 15 subjects, who meet the criteria for a clinical diagnosis of CM with documented growth as defined in Inclusion Criteria 5C, will enter Cohort 12 and receive two cycles of AU-011 treatment (each cycle will be comprised of 3 repeat 80 µg doses, each followed by 2 repeat laser applications). Cycle 2 of AU-011 will be administered as 3 repeat 80 µg doses, each followed by 2 repeat laser applications no earlier than the Week 12 Visit and after resolution of any inflammation resulting from the first cycle or when the inflammation is minimal and decreasing based on investigator judgement. Cycle 2 should be administered as soon as reasonably possible after inflammation has resolved or is minimal and decreasing based on investigator judgement. If the fovea is near the tumor edge, an adjustment to the laser procedure should be performed on each treatment day of both cycles as outlined in section 8.2.2 and the Injection and Laser Procedure Manual.

If 2 subjects experience a DLT during treatment with Cycle 2, as defined in Section 8.4.1., then no further subjects will receive Cycle 2 of AU-011 until discussed with the independent ocular oncologist and medical monitor and continuation of enrollment is confirmed.

Study Methods:

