The first expansion cohort (Cohort 9) is designed to establish the preliminary efficacy of AU-011 delivered at the highest dose that is safe and well tolerated from the escalation phase of the trial. Cohort 10 is designed to provide estimates of growth rates in observation subjects and Cohort 11 is designed to demonstrate the safety and tolerability of administering two 3-week treatment cycles of AU-011. Cohort 12 is designed to evaluate the efficacy and safety of AU-011 in subjects with documented growth who are similar to the planned Phase 3 population.

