Once the last subject in the expansion cohort has been enrolled and safety of the maximum safe and feasible dose is confirmed, approximately 6 additional subjects, who fulfil the criteria for the clinical diagnosis of CM, but without documented growth, will be enrolled into an observation cohort (Cohort 10). These subjects will be assessed every 3 months (ie, 90 day (+/- 7 days) intervals from the Screening Visit) until tumor growth of the CM lesion is established (as defined in Section 8.3.4.) and at which time will then receive treatment with AU-011, as 3 repeat 80 µg doses, each followed by 2 repeat laser applications and move to the same visit schedule as subjects entering the trial and receiving treatment with AU-011 immediately. These subjects will receive Cycle 2 of AU-011 administered as 3 repeat 80 µg doses, each followed by 2 repeat laser applications no earlier than the Week 12 Visit and after resolution of any inflammation resulting from the first cycle or when the inflammation is minimal and decreasing based on investigator judgement. Cycle 2 should be administered as soon as reasonably possible after inflammation has resolved or is minimal and decreasing based on investigator judgement. If the fovea is near the tumor edge, an adjustment to the laser procedure should be performed on each treatment day of both cycles as outlined in section 8.2.2 and the Injection and Laser Procedure Manual.

In addition, approximately 6 further subjects, who meet the criteria for a clinical diagnosis of CM, with or without documented growth, will enter Cohort 11 and receive two cycles of AU-011 treatment (each cycle will be comprised of 3 repeat 80 µg doses, each followed by 2 repeat laser applications). Cycle 2 of AU-011 will be administered as 3 repeat 80 µg doses, each followed by 2 repeat laser applications no earlier than the Week 12 Visit and after resolution of any inflammation resulting from the first cycle or when the inflammation is minimal and decreasing based on investigator judgement. Cycle 2 should be administered as soon as reasonably possible after inflammation has resolved or is minimal and decreasing based on investigator judgement. If the fovea is near the tumor edge, an adjustment to the laser procedure should be performed on each treatment day of both cycles as outlined in section 8.2.2 and the Injection and Laser Procedure Manual.

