The intention is to alternate the enrolment of Cohorts 10 and 11. If during the enrollment of these subjects, a subject has just been enrolled into Cohort 11 and a subject with documented growth presents, then that subject may instead be enrolled into Cohort 11 rather than Cohort 10 for which they would not be eligible due to the presence of documented growth and instead will be assigned to receive the first of 2 cycles of AU-011.

If 2 subjects experience a DLT during treatment with Cycle 2, as defined in Section 8.4.1., then no further subjects will receive Cycle 2 of AU-011 until discussed with the independent ocular oncologist and medical monitor and continuation of enrollment is confirmed.

Subjects with Documented Growth

Enrollment in Cohorts 10 and 11 was closed following approval of protocol revision 11 (Rev-11) at each site. An additional cohort, Cohort 12, of subjects with minimum defined levels of documented growth will be initiated to allow assessment of safety and efficacy of 2 cycles of AU-011 treatment in this key subgroup of subjects with CM. Since Cohort 12 has the same dose as Cohort 11 no safety review will be required.

Up to 15 subjects, who meet the criteria for a clinical diagnosis of CM with documented growth as defined in Inclusion Criteria 5C, will enter Cohort 12 and receive two cycles of AU-011 treatment (each cycle will be comprised of 3 repeat 80 µg doses, each followed by 2 repeat laser applications). Cycle 2 of AU-011 will be administered as 3 repeat 80 µg doses, each followed by 2 repeat laser applications no earlier than the Week 12 Visit and after resolution of any inflammation resulting from the first cycle or when the inflammation is minimal and decreasing based on investigator judgement. Cycle 2 should be administered as soon as reasonably possible after inflammation has resolved or is minimal and decreasing based on investigator judgement. If the fovea is near the tumor edge, an adjustment to the laser procedure should be performed on each treatment day of both cycles as outlined in section 8.2.2 and the Injection and Laser Procedure Manual.

If 2 subjects experience a DLT during treatment with Cycle 2, as defined in Section 8.4.1., then no further subjects will receive Cycle 2 of AU-011 until discussed with the independent ocular oncologist and medical monitor and continuation of enrollment is confirmed.

Study Methods

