8.4.2. Dose Escalation / Termination

Dose escalation to the next higher dose level, repeat dose group, repeat laser application or repeat cycle will be implemented only if less than 2 subjects in the prior cohort complete the treatment without a DLT.

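### No review of Cohort 11's second-cycle safety data is tied to Cohort 12: the waiver rests on equal dose, although the new exposure is the second cycle

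*Protocol*

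**What the plan says.** The waiver appears in two forms. Protocol section 6.1, under Subjects with Documented Growth, reads "Since Cohort 12 has the same dose as Cohort 11 no safety review will be required". The synopsis is narrower: "Since Cohort 12 has the same dose as Cohort 11 no additional safety review will be required prior to initiating this cohort". SAP section 3.2 follows the synopsis.

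Cohort 12 is to take "Up to 15 subjects, who meet the criteria for a clinical diagnosis of CM with documented growth", and gives them two cycles of the regimen used in Cohort 11. For that earlier cohort the plan was that "approximately 6 further subjects, who meet the criteria for a clinical diagnosis of CM, with or without documented growth, will enter Cohort 11". Its purpose is given in section 4.6: "Cohort 11 is designed to demonstrate the safety and tolerability of administering two 3-week treatment cycles of AU-011". The change from one cohort to the other is administrative: "Enrollment in Cohorts 10 and 11 was closed following approval of protocol revision 11 (Rev-11) at each site". In both cohorts Cycle 2 is given at the Week 12 visit at the earliest, once inflammation has cleared or is minimal and falling.

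Section 8.4.2 includes the repeat cycle among the escalation steps: a "repeat cycle will be implemented only if less than 2 subjects in the prior cohort" finish treatment free of a DLT. As worded, that condition looks inverted.

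Two further provisions matter. Under section 10.2.3 the medical monitor and the independent ocular oncologist look at AEs and SAEs across cohorts, monthly early in the study and six-monthly in follow-up. Under sections 6.1 and 8.2.1, two subjects with a DLT in Cycle 2 suspend further Cycle 2 treatment until the matter has been discussed with them.

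**The concern.** The waiver argues from dose, but dose does not separate Cohorts 11 and 12 from what had already been reviewed. The second cycle does. Pointing to Cohort 11 supports the waiver only if someone has looked at Cohort 11's Cycle 2 data, and no section requires that to happen at any point relative to Cohort 12.

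At stake is whether the largest two-cycle cohort proceeds to its second cycle on the strength of a considered look at the cohort set up to test it, or by default. Effects that appear some time after Cycle 2 matter most. Section 10.3.10 follows peri-tumoral whitening and pigmentary changes for 26 weeks after the last treatment of a cycle, well beyond the treatment days themselves.

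**Working it through.** The plan states no error rate, power or DLT rate for this rule, so there is no figure to reproduce. The check is mainly one of text, with some illustrative arithmetic.

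**1. Which transitions have a review attached (protocol section 6.1)**

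- Cohorts 2 and 3: a review one week after the last subject in the preceding cohort completes treatment.
- Cohorts 4 to 7: a review one day after the preceding cohort completes treatment.
- Cohort 8: a review one day after Cohort 7 and four weeks after Cohort 6.
- Cohort 9: a review four weeks after the last Cohort 8 treatment, expressly including EDI-OCT.
- Cohorts 10 and 11: safety of the maximum safe and feasible dose must be confirmed. Section 6.1 defines that regimen in terms of one cycle.
- Cohort 12: waived.

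Every step up to two cycles therefore has a review or confirmation, and all of them draw on one-cycle data. None is placed on two-cycle data.

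**2. The two waiver wordings.** Section 6.1 waives safety review without qualification. The synopsis and SAP section 3.2 waive an additional review before the cohort is initiated. The second form is compatible with a review between initiation and Cycle 2; the first, read literally, is not.

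**3. Whether the periodic review fills the gap.** Its early, monthly phase has no stated end. In the later phase the interval is six months, about 26 weeks, and the earliest Cycle 2 is at Week 12. A Cohort 12 subject who enters just after a six-monthly review could reach Cycle 2 about 26 − 12 = 14 weeks before the next one. Section 10.2.3 links this review to no decision to proceed.

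**4. Size of the group.** The planned two-cycle subjects are about 6 (Cohort 10) + about 6 (Cohort 11) + up to 15 (Cohort 12) = 27. Cohort 12's share is 15/27 = 56%. This assumes that every Cohort 10 subject shows growth and is treated; if none does, the share is 15/21 = 71%.

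**5. What small numbers can show.** The true Cycle 2 DLT rate *p* is an assumption, since the documents give none. The chance of at least two DLTs in *n* subjects is 1 − (1 − p)^n − n·p·(1 − p)^(n−1):

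| Assumed *p* | 6 subjects (Cohort 11) | 21 subjects (Cohorts 11 and 12) |
|---|---|---|
| 5% | 0.033 | 0.283 |
| 10% | 0.114 | 0.635 |
| 20% | 0.345 | 0.942 |
| 33% | 0.642 | 0.997 |

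With no DLT in *n* subjects, the one-sided 95% upper bound on the rate is 1 − 0.05^(1/n): 39% for n = 6 and 63% for n = 3.

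The pause on its own would often stay silent in Cohort 11 at rates that would matter. The bounds describe what a cohort of this size can exclude. They would be the same with or without a review, so they do not measure the effect of the waiver.

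**The case against.** The strongest reply is that two-cycle safety is watched. Section 10.2.3 provides for periodic review within and between cohorts and for review of DLT determinations. Section 10.2.3.3 has all AEs and SAEs in Cohorts 10 to 12 reported through the last visit, and section 10.2.3.5 sends SAEs to the sponsor within 24 hours. Section 10.3.10 asks investigators to notify the sponsor of whitening or pigmentary changes at any time. The pause stops further Cycle 2 treatment, and the DLT definition in section 8.4.1 carries no time limit of its own. All of this stands. A reader might infer that nobody looks at Cohort 11's second cycle, or that late harms set nothing in motion; the documents do not support either reading.

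A reader might also infer that opening Cohort 12 breaches section 8.4.2. That is not clear from the text. Its repeat-cycle step is most naturally the move from one cycle (Cohorts 8 and 9) to two (Cohorts 10 and 11). Cohort 12 repeats Cohort 11's whole regimen, so it expands a step already taken.

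Nor do the documents show how many Cohort 11 subjects had finished Cycle 2 when Cohort 12 began, since no accrual dates are given. Section 8.3.3 also allows additional therapy at the same regimen after Week 12 in other cohorts, so some experience of repeat courses may lie outside Cohort 11; its extent is not stated. Finally, SAP section 4.2 records early termination and the SAP introduction a first database lock on 25 Aug. 2021, so the scope for changing conduct may have passed.

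None of this supplies the missing link. The general safeguards react to events or run to a calendar. None requires Cohort 11's Cycle 2 data to be considered at a point defined by Cohort 12's progress.

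**Conclusion.** The point holds as a moderate gap in safety oversight together with a conflict of wording. No dedicated review of Cohort 11's Cycle 2 data is tied to Cohort 12, and the reason given, equal dose, does not address the exposure that is new. Up to 15 of about 27 planned two-cycle subjects (56%) are affected, assuming the planned cohort sizes are filled and all of Cohort 10 is treated. What remains is AE and SAE reporting, a periodic review that may be only six-monthly, and a two-DLT pause whose wording may or may not reach events that emerge after the last Cycle 2 treatment. The DLT probabilities rest on assumed rates and serve only to show that about six subjects give limited reassurance. The documents do not show that harm occurred, or that Cohort 12 was treated without regard to Cohort 11.

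**What to change.** Reconcile the synopsis, protocol section 6.1 and SAP section 3.2 with protocol sections 4.6, 8.4.2 and 10.2.3:

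- Make the waiver read the same in all three places, on grounds that address the second cycle as well as the dose.
- State how the review of Cohort 11 Cycle 2 data by the existing medical monitor and independent ocular oncologist is timed relative to Cycle 2 in Cohort 12.
- Clarify which transition the repeat-cycle step in section 8.4.2 covers, and resolve its condition, which appears inverted.
- Say whether the two-DLT pause is meant to include events that arise after the last Cycle 2 treatment.

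These are requests for consistency; the choice of clinical rule remains with the sponsor.

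The cost is protocol and SAP wording plus one more review, using people already appointed and data already collected. Because Cycle 2 comes no earlier than Week 12, enrolment and Cycle 1 in Cohort 12 need not wait. The downside is a possible short delay to the first Cycle 2 in that cohort. If Cohort 12 has already been treated, the study report can instead state when Cohort 11's Cycle 2 data were reviewed relative to Cohort 12's second cycle.

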6.2. Criteria for Study Termination

The Sponsor may suspend or terminate the study at any time for any reason. If the Investigator suspends or terminates the study at their site, the Investigator will promptly inform the Sponsor and the Institutional Review Board (IRB) and provide them with a detailed written explanation. The Investigator will also return all study drug and other materials to the Sponsor as required. Upon study completion, the Investigator will provide the IRB with notice of closure.

7. SELECTION AND WITHDRAWAL OF SUBJECTS

To be eligible for this clinical study, subjects must provide written informed consent and meet all of the inclusion criteria and none of the exclusion criteria.

7.1. Subject Inclusion Criteria

Subjects must:

- 1. Be at least 18 years of age of either gender or any race.
- 2. Have been informed about the nature and requirements of the study, voluntarily agreed to participate in the study, and documented this by signing the Informed Consent Form (ICF) before participating in any study-related activities.
- 3. Be willing and able to follow all instructions and attend all study visits.
- 4. Per the expert opinion of the Investigator, have clinically diagnosed primary CM with no known metastatic disease.
- 5. Have clinically diagnosed primary CM:
 - A. with tumor thickness of ≥ 1.2 mm and ≤ 3.0 mm on B-scan ultrasound and with a largest basal diameter of ≤ 13.0 mm on fundus photos associated with tumor growth,

OR

- B. with tumor thickness of ≥ 2.0 mm and ≤ 3.0 mm on B-scan ultrasound and with a largest basal diameter of ≤ 13.0 mm on fundus photos associated with the presence of subretinal fluid by OCT AND at least one of the following:
 - a. Overlying orange pigment (lipofuscin) on fundus photos
 - b. Vision loss
 - c. Flashes or floaters

OR

C. Criteria for Cohort 12: with tumor thickness of ≥ 0.5 mm and ≤ 3.0 mm on B-scan ultrasound, a largest basal diameter of ≤ 13.0 mm on fundus photos with an estimated tumor volume ≤ 50 mm³ associated with tumor growth within 2 years of screening (defined as ≥ 0.4 mm increase based on intersite measurements or ≥ 0.3 mm based on within site measurements on tumor thickness)

NOTE: Whenever available at the investigative site or referring site, historical images (B-scans and/or color fundus photos) for all subjects should be provided to the Independent Reading Center at the time of entry to the study. The investigative site should make all reasonable efforts to obtain this information from referring sites.

- 6. In the opinion of the treating physician, the subject could be managed by interventional therapy, or by cautious observation.
- 7. Be treatment-naïve for their primary CM.

- 8. Have a tumor for which the entire extent must be able to be imaged on required fundus photography in a single frame and treated by the laser.
- 9. If female and capable of becoming pregnant, agree to have pregnancy testing performed at screening (must be negative) and if required at Visit 2 (must be negative); must not be lactating; and must agree to use a medically acceptable form of birth control before administration of the investigational product and for three months after administration of the investigational product. Women considered capable of becoming pregnant include all females who have experienced menarche and have not experienced menopause (as defined by amenorrhea for greater than 12 consecutive months) or have not undergone successful surgical sterilization (hysterectomy, bilateral tubal ligation, or bilateral oophorectomy).
- 10. For women of childbearing potential and for males with sexual partners of childbearing potential: Acceptable forms of birth control are spermicide with barrier, oral contraceptive, injectable or implantable method of contraception, transdermal contraceptive, intrauterine device, or surgical sterilization of partner. For non-sexually active females and males, abstinence will be considered an acceptable form of birth control.
- 11. Be otherwise in good general health, with no significant or uncontrolled medical conditions, as determined by the Investigator.
- 12. Be able and willing to avoid all prohibited medications for the appropriate washout period (See Section 8.3.2).

7.2. Subject Exclusion Criteria

Subjects must not:

- 1. Have known contraindications or sensitivities to IRDye®700DX phthalocyanine-based dye, or laser in the study eye.
- 2. Have any ocular condition in the study eye that, in the Investigator's opinion, could affect the subject's safety or trial parameters.
- 3. Have a CM that invades or encompasses the optic nerve that precludes treatment, as determined by the investigator and/or shows extraocular extension.
- 4. Have metastatic disease confirmed by abdominal and chest imaging within three months prior to screening.
- 5. Have undergone vitrectomy at any time or have undergone any ocular surgical intervention in the study eye within three months before Visit 1, or are planning/will require ocular surgery in the study eye prior to the study drug administration. If the subject is likely to require cataract surgery in the study eye at any time prior to the Week 104 visit, he/she should not be enrolled.
- 6. Have a history of rhegmatogenous retinal detachment, diabetic retinopathy, or other active retinal disease in the study eye unrelated to the CM.
- 7. Have any active ocular disease in the study eye (other than CM) that may progress during the study and result in a change in vision or loss in vision (e.g., clinically significant

corneal dystrophies, keratoconus, glaucoma or clinically significant retinal or macular disease).

- 8. Have an active ocular infection (bacterial, viral, or fungal).
- 9. Use or require use of heparin or low molecular weight heparins within one week of treatment.
- 10. Use or require use of immunosuppressive or antineoplastic medications within five half-lives of Visit 1. Steroids, including inhalation steroids, are permitted.
- 11. Have previously received HPV vaccination.
- 12. Any active malignancies other than CM, or squamous or basal cell skin cancer. If there is evidence of clinical remission for at least one year, the subject's eligibility may be discussed with the medical monitor.
- 13. Have any significant illness (e.g., an uncontrolled autoimmune disease, severe cardiovascular disease [confirmed by a cardiologist], active infection, etc.) that the Investigator determines could interfere with study participation or safety, or put the subject at any unnecessary risk.
- 14. Have planned or will require systemic surgery during the active study treatment period.
- 15. Have used an investigational drug or medical device within 30 days or 5 half-lives of Visit 1 or be concurrently enrolled in another investigational product trial.

